#### WP2 Process evaluation

The process evaluation will be qualitative semi-structured interviews with stakeholders (tenants, landlords, implementers and representatives of stakeholder organisations); a national and a local workshop; document analysis.

### WP3 Cost-benefit analysis using subjective wellbeing approach

The economic evaluation will produce a cost-benefit analysis that uses the subjective wellbeing approach to monetise the benefits of SL. The starting point for the calculation of the benefits of SL will be the estimate of the impact of SL on the life satisfaction variable from the APS, one of our individual-level outcome measures. We will then follow the procedure described in Dolan et al. (2019) [35].

Essentially, we will use an estimate of the impact of income on life satisfaction from previous research to determine the income change that would be required to achieve the same change in life satisfaction as achieved by SL. Multiplying this income change amount by the number of individuals affected by SL will provide the total benefit of SL from a societal perspectives. All our calculations will be retrospective and estimate the benefits of SL over our 2012 to 2019 sample period. Depending on the results of our analysis of spillover effects, we will adjust the benefit estimate accordingly.

We will calculate the costs of SL from a public sector perspective and attempt to estimate the costs of SL from a societal perspective. To determine the total cost of SL from a public sector perspective over the 2012 to 2019 sample period, we will measure the direct and indirect cost of SL in four case study sites. Accounting data provided by the case study sites will be the starting point for the cost calculation. However, the economic concept of opportunity cost goes beyond accounting cost. For example, local authorities might employ staff specifically for the administration of the SL schemes in their area, so these costs would be included in the accounting data as staff salaries and on-costs. However, staff not specifically employed for SL purposes might also be involved in administering local schemes. Any staff involved in SL will require office space and might need to be trained and supervised. Local authorities need to disseminate information about their SL schemes using their website or other means and maintain the online application system. All these activities incur costs, either directly in the form of money being handed over in payment or indirectly in the form of resources such as staff time or office space not being available for alternative uses.

The four case study sites have been selected to represent different types of SL (smaller and larger) in different regional contexts (north and south). We will use extrapolation methods that use these two broad characteristics as well as cost information obtained through FOI requests to assign costs to the other local authorities that have implemented SL. We will subtract income from license fees, fines and civil penalties to obtain net costs.

In addition, we will estimate the potential costs saved by the NHS through SL's impact on antidepressant prescribing, mental-health related hospital admissions and all-cause hospital admissions over our sample period. If possible, we will also estimate potential cost savings through impacts on mental health-related benefits. If we find substantial cost savings, we will subtract these from the cost of SL to local authorities to obtain net costs from a public sector perspective.

To estimate net costs from a societal perspective we will add back in any income local authorities generate from license fees, fines and civil penalties and try to estimate the costs landlords incur to remove hazards following the receipt of an improvement notice issued by the local authority following an SL inspection.

#### WP4: Knowledge exchange

Knowledge exchange workshops with our policy and practice links, including charities (Shelter, Crisis, Safer Renting), national government, local and regional government, practice and research networks.

### 9b. Study setting

WP1 and WP3 will examine impacts across England.

WP2 will include studies of four sites where local authorities have implemented SL schemes. Two in the north of England and two in the south of England: including a larger and smaller scheme in the north and also in the south. Liverpool (larger scheme, north), Gateshead (smaller scheme, north), Newham (larger scheme, south), and Islington (smaller scheme, south) local authorities have expressed interest in taking part.

# 10. Study schedule

Start date: 1st December 2023 (see Gantt chart, Fig. 3, Appendix I)

Length: 26 months.

- 0-3 months: ethics approval, PPI & AG meetings.
- 2-6 months: WP1 update data, submit protocol; WP2 begin recruitment and data collection.
- 7-17 months: WP1 Analysis plan and analysis; WP2 data collection; WP3 prepare data
- 18-22 months: All WPs: Analysis, interpretive workshops; refine and begin write-up
- 22-26 months: final analysis and write-up.

# 11. Sample size

#### *Individual-level outcomes*

For the individual-level outcome measures, we estimate that the APS includes about 1,000 respondents per year who live in private rented accommodation in LSOAs covered by SL schemes, so over our 2012 to 2019 sample period we expect to observe around 8,000 individuals in the intervention group (5.5% of the England population live in the schemes included in the study). The number of APS participants in the matched comparison LSOAs will be approximately 3000 per year if we match 3 control LSOAs to every intervention LSOA.

As the power calculation for our staggered treatment timing difference-in-differences design with repeated cross-section data would be very complicated, we ran a power calculation for the canonical difference-in-difference design with one pre- and one post-intervention observation to get a broad idea of the statistical power of our analysis. The power calculations are based on a bootstrapping algorithm with 1,000 repetitions with 95% significance level and a 3:1 ratio between control to intervention units. The outcome variable was designed as normal-distributed and z-standardised in an artificial dataset. With just 1,000 respondents – the potential annual number of respondents in treated areas – the minimum detectable difference would be 30% of an SD (Table 1).

Table 1 Power calculations based on bootstrapping algorithm with 1,000 repetitions for a DiD design with 95% significance level, one pre- and one post-intervention observation, and 3:1 ratio between control to intervention units (Burlig et al. 2020) [36]. The outcome variable was designed as normal-distributed and z-standardised. Cells shaded in grey indicate power calculations at or above 80%. A unit can correspond to either a respondent or a LSOA area depending on the context. N corresponds to the number of treated units.

| N    | 10%SD | 15%SD | 20%SD | 25%SD | 30%SD |
|------|-------|-------|-------|-------|-------|
| 1000 | 0.167 | 0.291 | 0.523 | 0.694 | 0.837 |
| 1500 | 0.195 | 0.440 | 0.637 | 0.864 | 0.953 |
| 2000 | 0.272 | 0.540 | 0.800 | 0.934 | 0.989 |
| 2500 | 0.333 | 0.659 | 0.884 | 0.972 | 0.997 |
| 3000 | 0.379 | 0.706 | 0.923 | 0.987 | 0.998 |
| 3500 | 0.423 | 0.787 | 0.958 | 0.989 | 1.000 |
| 4000 | 0.515 | 0.833 | 0.979 | 0.997 | 1.000 |
| 4500 | 0.568 | 0.876 | 0.988 | 0.999 | 1.000 |
| 5000 | 0.593 | 0.894 | 0.993 | 0.998 | 1.000 |
| 5500 | 0.652 | 0.930 | 0.993 | 1.000 | 1.000 |
| 6000 | 0.685 | 0.946 | 1.000 | 1.000 | 1.000 |
| 6500 | 0.727 | 0.962 | 0.998 | 1.000 | 1.000 |
| 7000 | 0.767 | 0.973 | 1.000 | 1.000 | 1.000 |
| 7500 | 0.755 | 0.982 | 1.000 | 1.000 | 1.000 |
| 8000 | 0.797 | 0.986 | 1.000 | 1.000 | 1.000 |
| 8500 | 0.811 | 0.992 | 1.000 | 1.000 | 1.000 |

| 9000  | 0.839 | 0.994 | 1.000 | 1.000 | 1.000 |
|-------|-------|-------|-------|-------|-------|
| 9500  | 0.850 | 0.994 | 1.000 | 1.000 | 1.000 |
| 10000 | 0.870 | 0.999 | 1.000 | 1.000 | 1.000 |

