 $Y_{iat}$  indicates one of our outcome measures for individual i in LSOA a in year t.  $\alpha_a$  is an LSOA effect, which accounts for time-invariant differences between the LSOAs, and  $\varphi_t$  is a year effect, which accounts for changes over time happening in all LSOAs.  $D_{at}$  takes the value 1 if LSOA a is subject to an SL scheme in year t and 0 otherwise.  $\beta$  is the treatment effect, i.e. it captures the impact of the SL scheme. In the special case of only two years t (before and after the intervention) the ordinary least squares (OLS) estimate  $\hat{\beta}$  is equivalent to the difference-in-differences estimate  $\hat{\gamma}$ :

$$\hat{\gamma} = \left( \overline{Y}_{SL,AFTER} - \overline{Y}_{SL,BEFORE} \right) - \left( \overline{Y}_{COMPARATOR,AFTER} - \overline{Y}_{COMPARATOR,BEFORE} \right)$$

 $\bar{Y}_{SL,AFTER}$  is the mean of the outcome measure in the LSOAs with an SL scheme after implementation of the SL scheme and  $\bar{Y}_{SL,BEFORE}$  is the mean before implementation.  $\bar{Y}_{COMPARATOR,AFTER}$  is the mean of the outcome measure in the matched comparator LSOAs in the year after SL was implemented in the SL areas and  $\bar{Y}_{COMPARATOR,BEFORE}$  is the mean in the year before implementation. Unfortunately, this intuitive causal interpretation of the parameter estimate  $\hat{\beta}$  is unlikely to apply in the more general case of more than two years t and the intervention being rolled out over several years. As the implementation of SL schemes is at the discretion of local authorities, they have been rolled out at different times over many years.

In this setting with staggered intervention timing the OLS estimator of  $\beta$  in the canonical two-way fixed effects regression yields an unbiased estimate of the treatment effect only if there is no treatment effect heterogeneity, i.e. if all LSOAs have the same treatment effect and if the treatment has the same effect regardless of how long it has been since the treatment started. The bias occurs because the OLS estimator is a weighted average of comparisons between treated and not-yettreated units as well as between treated and already-treated units. If, for example, the treatment effect gets stronger over time, the parallel trends assumption discussed above does not hold for the latter comparison [27,28].

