### Area-level outcomes

For the area-level outcomes, our main analysis will examine 1,635 treated LSOAs, which would give a minimum detectable difference of 25% of an SD (Table 1).

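### Licensing is decided by 41 local authorities of very unequal size, but neither document plans inference above the LSOA or the respondent

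*Protocol*

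**What the plan says.** Section 9a (individual-level outcomes) states that "the implementation of SL schemes is at the discretion of local authorities". The Protocol summary counts 41 authorities, 61 schemes and 1,635 LSOAs. Section 9a then sets out models with LSOA and year effects, estimated by Callaway and Sant'Anna's method, with synthetic difference-in-differences as the alternative. Section 18 adds non-linear models, and matches LSOAs within three super-regions. Neither document names a standard-error method, a clustering level or an authority-level term.

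Section 11 describes a simplified power calculation "with 95% significance level and a 3:1 ratio between control to intervention units", with "one pre- and one post-intervention observation to get a broad idea of the statistical power of our analysis". On the data used it says: "The outcome variable was designed as normal-distributed and z-standardised in an artificial dataset". The Table 1 caption adds "A unit can correspond to either a respondent or a LSOA area depending on the context" and "N corresponds to the number of treated units". At area level, "our main analysis will examine 1,635 treated LSOAs", for which the plan quotes a minimum detectable difference of 25% of an SD. Section 18 applies a 5% false discovery rate to the secondary analyses.

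**The concern.** The decision to license, its timing and its enforcement are shared by the LSOAs of a scheme, and often of a whole authority. So are other local changes that have nothing to do with licensing. If LSOA changes are correlated within authorities, 1,635 LSOAs carry much less information than 1,635 independent units. Matching within super-regions does not remove a shock specific to one authority.

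A change confined to one or two large authorities could then look like a precisely estimated licensing effect. The Protocol gives a reason to take this seriously. Section 7b reports that the SAMHI result of the London study was driven by that city's largest scheme, in the main Olympic setting, and SAMHI is the primary area-level outcome here. P-values that are too small would also enter the false discovery rate step, which cannot repair them.

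**Working it through.** **Inputs.** Two-sided alpha of 0.05 (sidedness is not stated) and 80% power, the threshold for shading in Table 1, so the multiplier is 1.96 + 0.84 = 2.80. Outcome SD 1, three controls per treated unit, cluster sizes from Table S1. The intra-authority correlation (ICC) of LSOA changes is not in the documents; 0.01, 0.02 and 0.05 are assumptions.

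**1. Reproducing Table 1.** With independent units and uncorrelated pre and post values, a change has variance 2, and power = Φ(δ/SE − 1.96).
- N as treated units, as captioned: SE² = 2(1/N + 1/3N) = 2.667/N.
- N as treated plus control units: SE² = 2(4/N + 4/3N) = 10.667/N.

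| N, effect | Printed | N = treated | N = total |
|---|---|---|---|
| 1000, 30% SD | 0.837 | 0.9999 | 0.828 |
| 1500, 25% SD | 0.864 | 1.000 | 0.843 |
| 2000, 20% SD | 0.800 | 0.9998 | 0.782 |

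Reading N as the total matches 84 of 95 cells within 2 points; the captioned reading matches 50. Table 1 therefore fits independent units with no cluster term, and its N behaves as the total. For 1,635 treated plus 4,905 controls the independent-unit figure is 2.80 × √(2.667/1635) = 11.3% SD. With 1,635 as the total it is 2.80 × √(10.667/1635) = 22.6%, and the next column up is 25%.

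**2. Cluster sizes.** Summing Table S1 by authority gives 41 authorities. The six largest are Liverpool 298, Croydon 220, Newham 155, Waltham Forest 144, Nottingham 135, and Barking and Dagenham 110: 1,062 in all, and 1,062/1,635 = 65%. With Σm² = 235,809:
- size-weighted mean = 235,809/1,635 = 144.2;
- effective clusters = 1,635²/235,809 = 11.3.

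Section 18 names the 100%-coverage set as the main analysis in its text, and the 5–100% set in the Table 2 caption. For the 100% set, 21 authorities remain with Σm² = 214,556, and 1,356²/214,556 = 8.6 effective clusters.

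**3. False-positive rate of an LSOA-level test.** Assume 2,819 unique controls, equally weighted and spread evenly over G authorities. The naive variance is V₀ = 1/1,635 + 1/2,819 = 0.000966. With Σm²/1,635² = 0.0882, the true variance is V = ICC × (0.0882 + 1/G) + (1 − ICC) × V₀. The rejection rate under the null is 2Φ(−1.96√(V₀/V)). For ICC 0.02 and G = 100: V = 0.02 × 0.0982 + 0.98 × 0.000966 = 0.00291, √(V₀/V) = 0.576, rate 25.9%.

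| ICC | G = 100 | G = 200 |
|---|---|---|
| 0.01 | 16.6% | 16.1% |
| 0.02 | 25.9% | 25.1% |
| 0.05 | 42.5% | 41.5% |

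Simulation under the same assumptions agrees.

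**4. Detectable difference with clustering.** Design effect = 1 + 143.2 × ICC, applied to both arms, starting from 11.3% SD.

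| ICC | Design effect | Detectable difference |
|---|---|---|
| 0.01 | 2.43 | 17.6% SD |
| 0.02 | 3.86 | 22.2% SD |
| 0.05 | 8.16 | 32.3% SD |

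The printed 25% is reached at a design effect of (25/11.3)² = 4.9, so ICC = 3.88/143.2 = 0.027. The threshold is about 0.036 if only the treated arm is clustered, and about 0.10 if all authorities had the mean of 39.9 LSOAs.

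**The case against.** The strongest reply is that silence about standard errors is not a plan to use unclustered ones. That is right, and the rejection rates above are conditional on testing at LSOA level. A reader might infer that the analysts will accept software defaults, but neither document says what those would be. What remains is that every model is written at LSOA or respondent level, and nothing moves inference above it.

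A reader might also infer that the printed 25% SD is far too optimistic. The documents do not support that. The labelling of N in Table 1 works in the conservative direction and absorbs a design effect of up to about 4.9. This is an accidental offset, not an allowance for clustering. Section 11 also presents the calculation as a rough guide, and the sample already includes all eligible schemes, so power cannot change the design.

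A third tempting inference is that p-values are shown to be too small for both primary outcomes. No size is computed for APS anxiety. About 1,000 respondents a year are spread over 1,635 LSOAs, so the LSOA design effect cannot be carried across.

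Scheme is also a candidate cluster level: 15 of the 41 authorities have more than one start year in Table S1, and Section 18 lists only five schemes covering at least 90% of the authority's population. Clustering by scheme changes little (size-weighted mean 140.4). Finally, the plan has group-time effects, London and scheme-size subgroups, synthetic difference-in-differences and exposure falsification. These bear on heterogeneity and bias, and do not correct standard errors.

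**Conclusion.** The concern holds as a gap in planned inference. Treatment is decided by 41 authorities, equivalent to about 11 equal clusters, or about 9 across 21 authorities if the 100%-coverage set is the main analysis. Neither document plans inference above the LSOA or respondent. If area-level tests are run at LSOA level, a nominal 5% test would reject a true null in about 16%, 26% or 42% of cases. That rests on assumed ICCs of 0.01, 0.02 and 0.05 and on controls spread over 100 to 200 authorities. The individual-level concern is one of principle only.

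The power statement needs correcting but is not shown to be far too optimistic. With clustering, the detectable difference is about 18%, 22% or 32% SD at those ICCs, and the printed 25% is exceeded only above about 0.03. Correlation between pre and post values within an LSOA would lower these figures; reuse of controls would raise them slightly.

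**What to change.** In Sections 9a and 18, state before outcome analysis that standard errors for all estimators, at area and individual level, are clustered on local authority, with scheme-level clustering as a sensitivity analysis. Take p-values from a method suited to few, unequal clusters: a wild cluster bootstrap where the estimator allows it, or permutation of whole authorities, which would extend the exposure falsification in Section 17.

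In Section 11, correct the meaning of N in Table 1 and restate the detectable difference with a design effect over a stated ICC range. Use the LSOA count of whichever coverage set is confirmed as the main analysis.

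The cost is mostly wording and some computing time. The permutation version may need re-matching, because controls were matched LSOA by LSOA, with replacement, within super-regions. Confidence intervals will be wider.

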### Selection of control areas

Only areas that were untreated and did not qualify for any of the exclusion criteria were entered into the pool of control candidates (Table 2). SL schemes were only introduced in urban areas and rural LSOA11 were accordingly excluded from the matching pool.

Variables (LSOA11-level) for matching were proportions of the population in receipt of income benefits, self-reported non-white ethnicity, and proportions of households from the private rental sector, living in housing in poor condition, overcrowded, or unaffordable, whether buildings were mainly built before 1945 (Table 4). Skewed variables were logarithmically transformed (natural logarithm) prior to matching.

Propensity score matching (PSM) with 1:3 controls and replacement within each super region was used for the treatment (Table 4, Table S4) and spillover units (Table S5-S6) [53].

Table 4 Baseline characteristics for Treated, Never-treated, and propensity score matched control areas (1 treated:3 controls) with replacement. Number of standardised 2011 Lower Layer Super Output Area (LSOA11).

| A
Matching variables | B
Treated | C
Never-Treated | D
Matched Controls | E
Std. dif. (B-D) |
|-------------------------|--------------|--------------------|-----------------------|----------------------|
| THE NORTH               | N=470        | N=7,255            | N=1,410 (967 unique)  |                      |
| Age 0-15 years          | .18          | .19                | .18                   | .06                  |

| Age 16-59 years        | .63   | .58   | .64   | 07   |
|------------------------|-------|-------|-------|------|
| Ln(Income deprivation) | -1.42 | -2.04 | -1.47 | .06  |
| Ln(Private rental)     | -1.58 | -2.19 | -1.57 | 02   |
| Unaffordability        | .93   | 53    | .82   | .06  |
| Ln(Poor housing cond.) | -1.34 | -1.62 | -1.34 | <01  |
| Ln(Overcrowding)       | -2.56 | -3.09 | -2.59 | .05  |
| Ln(Non-White)          | -2.52 | -3.18 | -2.56 | .04  |
| Pre-1945 construction  | .76   | .45   | .76   | <.01 |
|                        |       |       |       |      |

| THE SOUTH              | N=235 | N=13,746 | N=705 (581 unique) |     |
|------------------------|-------|----------|--------------------|-----|
| Age 0-15 years         | .19   | .19      | .19                | 11  |
| Age 16-59 years        | .66   | .58      | .65                | .10 |
| Ln(Income deprivation) | -1.61 | -2.24    | -1.57              | 06  |

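### Table 1's power values fit N as total units, not treated units as captioned, so the stated detectable differences are about twice what the stated calculation gives

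*Protocol*

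**What the plan says.** Section 11 (Sample size) is the same in the protocol and the SAP on this point. It offers, as a rough guide, a power calculation for the "canonical difference-in-difference design with one pre- and one post-intervention observation". The method is a "bootstrapping algorithm with 1,000 repetitions with 95% significance level and a 3:1 ratio between control to intervention units", and the outcome is simple: "The outcome variable was designed as normal-distributed and z-standardised in an artificial dataset". The Table 1 caption defines the row label: "N corresponds to the number of treated units". It also says that shaded cells mark power of at least 80%.

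Two results are read from the table. For 1,000 treated-area respondents in a year, "the minimum detectable difference would be 30% of an SD (Table 1"). For the area-level outcomes, 1,635 treated LSOAs are entered, "which would give a minimum detectable difference of 25% of an SD (Table 1").

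On controls, Section 11 says: "The number of APS participants in the matched comparison LSOAs will be approximately 3000 per year", on condition that three control LSOAs are matched to each treated one. The abstract in both documents gives the same threefold ratio. Section 18 (Selection of control areas) reports what was done: "Propensity score matching (PSM) with 1:3 controls and replacement within each super region was used". Table 4 prints the distinct controls by region, and Table 3 gives their total, 2,819.

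**The concern.** With 1,000 treated units, 3,000 controls and an SD of 1, a difference-in-differences of 0.30 SD should be detected almost always, yet Table 1 prints 0.837. If the rows are mislabelled, both detectable differences were read from the wrong row. They are the only power figures in the plan, and they cover both primary outcomes, so a reader would take away a sensitivity that the stated calculation does not give. A separate, smaller question is whether the threefold control count in Section 11 describes the sample that matching produced.

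**Working it through.** **Inputs** (Section 11 and the Table 1 caption): SD 1; one pre and one post observation; 3 controls per treated unit; 5% significance; 80% power. The sides of the test and the pre/post correlation are not stated. I take two-sided and zero.

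**The plan's own reading.** Row 1000 first reaches 80% in the 30% column (0.837; 0.694 at 25%). For 1,635, row 1500 gives 0.637 at 20% and 0.864 at 25%. So 30% and 25% are correct readings of those rows if the caption is right.

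**Formulas.**
- SE = sqrt[2(1/nT + 1/nC)]
- Power = Φ(d/SE − 1.96) + Φ(−d/SE − 1.96)
- Detectable difference = (1.960 + 0.842) × SE

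If N is treated units (nT = N, nC = 3N), the variance is 8/(3N) = 2.667/N. If N is total units (nT = N/4, nC = 3N/4), it is 32/(3N) = 10.667/N. The variance is four times larger, so the SE is doubled.

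**Row 1000**

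| | 10% | 15% | 20% | 25% | 30% |
|---|---|---|---|---|---|
| Printed | 0.167 | 0.291 | 0.523 | 0.694 | 0.837 |
| N treated (1,000 + 3,000) | 0.491 | 0.828 | 0.972 | 0.998 | 1.000 |
| N total (250 + 750) | 0.161 | 0.306 | 0.491 | 0.677 | 0.828 |
| Simulation, 250 + 750, 4,000 repetitions | 0.172 | 0.302 | 0.493 | 0.672 | 0.820 |

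**All 95 cells**

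| Reading | Mean absolute gap | Largest gap | Cells within 0.02 |
|---|---|---|---|
| N treated | 0.121 | 0.54 | 50 |
| N total | 0.007 | 0.041 | 84 |

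The 50 agreeing cells in the first line do not discriminate, because power there is near 1. With 1,000 repetitions the Monte Carlo SE is up to sqrt(0.25/1000) = 0.016, so the gaps in the second line are broadly simulation noise. The table itself shows such noise: at 10% SD, power falls from 0.767 (row 7000) to 0.755 (row 7500).

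**Other readings.** I also tried splitting N between the pre and post samples, N as controls, 1:1 allocation, a post-only comparison, and one-sided versions of each. None fits: the root-mean-square error is 0.055 or more, against 0.011. The variance constant that best fits the table is 10.37. Keeping the caption would then need a pre/post correlation of 1 − 10.37/2.667 = −2.9, which is impossible.

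**Detectable differences with N as treated units**
- 1,000 + 3,000: SE = sqrt(2.667/1000) = 0.0516, giving 14.5% SD. Table 1 agrees once entered at the total of 4,000: 0.833 at 15%.
- 1,635 + 4,905: SE = sqrt(2.667/1635) = 0.0404, giving 11.3% SD. The total is 6,540; row 6500 gives 0.727 at 10% and 0.962 at 15%, so the grid answer is 15%.
- 1,356 at 3:1: SE = sqrt(2.667/1356) = 0.0443, giving 12.4% SD. This set matters because the text of Section 18 (Selection of treatment areas) makes full-coverage LSOAs the main analysis, while the Table 2 caption names the 5%–100% set.

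Like for like, N as total gives 28.9% for 1,000 and 22.6% for 1,635, exactly double 14.5% and 11.3%.

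**Controls** (Tables 3 and 4). Matched slots: 1,410 + 705 + 2,790 = 4,905 = 3 × 1,635. Distinct LSOAs: 967 + 581 + 1,271 = 2,819, and 2,819/1,635 = 1.72 (London 1,271/930 = 1.37). Re-using an LSOA adds no survey respondents. If respondents scale with distinct LSOAs (an assumption), 1,000 × 1.72 is about 1,700 control respondents a year. Then:
- Individual level: 2.802 × sqrt[2(1/1000 + 1/1724)] = 15.8% SD.
- Area level: 2.802 × sqrt[2(1/1635 + 1/2819)] = 12.3% SD.

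Both are best cases, because they weight every distinct control equally and the actual match weights are not given.

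**The case against.** The strongest reply is that nothing depends on the error. The data are secondary, the set of schemes is fixed, no recruitment target or decision rule uses Table 1, and Section 11 presents it only as a rough guide. The plan also understates power for the simple design, which is the safe direction. All of that stands, and it limits the importance of the point. It does not make the caption agree with the numbers under it.

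A second reply is that the cause is unknown. A variance four times larger, from an SD of 2 or a design effect of 4, would reproduce the table with N as treated units. Neither is stated, and an SD of 2 conflicts with a z-standardised outcome, but only the simulation code can settle it.

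Third, a reader might infer that the study can really detect 11% to 15% of an SD. The documents do not support that. With 1,635/41, or about 40, LSOAs per local authority and an assumed intra-authority correlation of the change of 0.01, 0.05 or 0.10, the factor sqrt(1 + 39 × ICC) is 1.18, 1.72 or 2.21. It turns 11.3% into 13%, 19% or 25%. This assumes equal-sized authorities, whereas schemes in Table S1 range from 1 to 298 LSOAs. Nor does this rescue the stated 25%, because Table 1 contains no clustering.

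On controls, the 3,000 is conditional, the distinct counts are disclosed, and 3:1 holds for weighted slots. A reader might infer that the matching failed or that 1,700 a year is a known count. Neither follows.

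**Conclusion.** The power statement is wrong as written. Under the stated inputs, the caption and Table 1 cannot both be right. The two detectable differences are about twice what the stated calculation gives: 30/14.5 = 2.07 and 25/11.3 = 2.21. Part of the second ratio comes from setting a grid value against a continuous one; on the table's grid it is 25/15 = 1.67. The result rests on zero pre/post correlation, a two-sided 5% test and independent units, and it holds for either candidate LSOA set.

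A reader might also infer that the figures will distort the interpretation of null results. Neither document says they will be used that way, so that is not part of the finding. The control count is secondary: 1.72:1 in distinct LSOAs raises the detectable differences by only about one percentage point of an SD, at best to 15.8% and 12.3%.

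**What to change.** 1. Check the simulation code. Unless it shows an unstated fourfold variance, correct the Table 1 caption in both documents so that N is total units, 25% of them treated. If it does show one, state it.
2. Settle which LSOA set is the main analysis (1,635 or 1,356), then restate both detectable differences in Section 11 of both documents. Under the stated inputs at 3:1 these are 14.5% SD for 1,000 treated respondents, and 11.3% SD for 1,635 LSOAs or 12.4% for 1,356.
3. Say beside them that they ignore local-authority clustering, staggered cohorts and the binary anxiety outcome, and so are best-case values.
4. In Section 11 and the abstract, say that 3:1 holds for weighted matched slots only. Replace the 3,000 a year and the threefold statement with the actual count of distinct control respondents.

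The cost is one check of existing code, one respondent count from the APS data, and wording. No new data are needed, and no analysis changes.
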